3.2.2 Secondary Study Endpoints

CONFIDENTIAL

This material is the property of the NYU Langone Health. Do not disclose or use except as authorized in writing by the study sponsor
Behavioral Intervention Template Version: 18 July 2022

The secondary endpoint, needed to fulfill Aim 2, is when the biospecimens have been analyzed for phthalate metabolites and bisphenols.

3.2.3 Exploratory Endpoints

N/A

4 Study Enrollment and Withdrawal

4.1 Inclusion Criteria

In order to be eligible to participate in this study, an individual must meet all of the following criteria:

1. Enrolled in NYU CHES study at the NYULH-Brooklyn campus
2. Over 18 years of age
3. At least 37 weeks gestation or <6 months postpartum
4. Carrying singleton fetus or having given birth to a singleton infant
5. Intending to breastfeed or breastfeeding
6. English or Spanish speaking
7. Intending to obtain/obtaining pediatric care for infant at the Sunset Park Family Health Center at NYU Langone

4.2 Exclusion Criteria

An individual who meets any of the following criteria will be excluded from participation in this study:

1. Not enrolled in NYU CHES study from the NYULH-Brooklyn campus
2. Under 37 weeks gestation or having had a preterm birth
3. Carrying multiples or having given birth to multiples
4. Not intending to breastfeed or not currently breastfeeding
5. Not comfortable communicating in English or Spanish
6. Not intending to obtain/obtaining pediatric care for infant at NYULH Sunset Park Family Health Center
7. Under 18 years of age

4.3 Vulnerable Subjects

This study includes pregnant women and neonates, who are vulnerable subjects. We do not anticipate that this study will pose greater than minimal risk to the mother, fetus, and later neonate, as both disposable and cloth diapers are commonly used among our study population. Additionally, collection of neonatal urine and maternal breast milk involves no more than minimal risk. Urine will be collected via a bag that gently adheres to the skin around the infant's penis; breast milk will be expressed manually by the participant. Participation in this study is entirely voluntary. Participants will be able to withdraw from the study at any time without negative consequences. Our study design is in compliance with all items included in 45 CFR part 46.204 (research involving pregnant women or fetuses) and 46.205 (research involving neonates.) Any risk to neonates is

CONFIDENTIAL

expressly in pursuit of benefits that would directly benefit them; i.e. regulation of chemicals in baby products. Furthermore, while this research does not hold out the prospect of benefit for the pregnant woman or the fetus, risk to the fetus is not greater than minimal and the purpose of the research is the development of important biomedical knowledge that cannot be obtained by any other means. A pregnant person's consent will be obtained in accord with the informed consent provisions of subpart A. The risk in this study is the least possible for achieving the objectives of the research. No inducements, monetary or otherwise, will be offered to terminate a pregnancy. Individuals engaged in the research will have no part in any decisions as to the timing, method, or procedures used to terminate a pregnancy. Individuals engaged in the research will have no part in determining the viability of a neonate.

4.4 Strategies for Recruitment and Retention

Potentially eligible participants will be identified by Diaper Study personnel from among those already enrolled in NYU CHES study at the Brooklyn campus. All Diaper Study personnel will be added to the NYU CHES study. Potential participants will be recruited either by phone or at an in-person prenatal visit at ≥37 weeks gestation or within 6 months postpartum.

- **Remote Screening**

- Potential participants will be contacted via phone using an IRB-approved telephone recruitment script. If they are interested in hearing more about the study, study staff will ask screening questions over the phone to confirm eligibility.
- If potential participants are eligible and still interested in learning more about the study, potential participants will be sent the REDCap link to the Key Information Sheet and Informed Consent and will be given the phone number of a study team member to call after they have reviewed the consent materials. Refer to Section 12.3.2 for more information on the consent procedures.
- If potential participants are not eligible and/or do not wish to take part in the study, their PHI (phone number, address, and any other PHI) will be discarded at this point.

- **In-Person Screening**

- If possible or preferred by the potential participant, screening may occur in person at the NYULH Brooklyn location. This will be coordinated by study staff.
- Study staff will give the potential participant a physical copy of the Key Information Sheet and Study Infographic if it has not already been sent to them. If the potential participant is interested, study staff will ask screening questions to confirm eligibility.
- If the potential participant is eligible and still interested in learning more about the study, the study staff member will walk the potential participant through Informed Consent. If the potential participant wishes to take part in this study, she will be asked to sign a paper copy of the Informed Consent. Refer to Section 12.3.2 for more information on the consent procedures.

In order to retain enrolled participants, we will visit them in the hospital following delivery or via phone call if a birth visit is not possible in order to inform participants of their group assignment and contact them again two weeks and six weeks after birth to check in on the diaper delivery logistics and assess and encourage group assignment adherence.

CONFIDENTIAL

4.4.1 Use of DataCore/Epic Information for Recruitment Purposes

This study will not use NYULH's DataCore/Epic information for recruitment purposes. We will use participant information from our ongoing study NYU CHES study for recruitment purposes.

4.5 Duration of Study Participation

The estimated time of enrollment is 1-3 weeks prior to delivery or within 6 months postpartum. Participants and their infants will be enrolled for three months.

4.6 Total Number of Participants and Sites

10 mother-infant pairs will be enrolled in this study. It is expected that all participants will provide usable data.

4.7 Participant Withdrawal or Termination

4.7.1 Reasons for Withdrawal or Termination

Participants are free to withdraw from the study at any time upon request and with no consequence.

An investigator may terminate participation in the study if:

- Any clinical adverse event (AE), laboratory abnormality, or other medical condition or situation occurs such that continued participation in the study would not be in the best interest of the participant.
- The participant meets an exclusion criterion (either newly developed or not previously recognized) that precludes further study participation.

4.7.2 Handling of Participant Withdrawals or Termination

If a participant withdraws between the time of consent and biospecimen collection, the participant will be replaced.

4.7.3 Premature Termination or Suspension of Study

This study may be temporarily suspended or prematurely terminated if there is sufficient reasonable cause. Written notification, documenting the reason for study suspension or termination, will be provided by the suspending or terminating party to the PI. If the study is prematurely terminated or suspended, the PI will promptly inform the IRB and will provide the reason(s) for the termination or suspension.

Circumstances that may warrant termination or suspension include, but are not limited to:

CONFIDENTIAL

- PI decision
- Insufficient compliance to protocol requirements

Study may resume once concerns about data quality are addressed and satisfy the sponsor and/or IRB.

5 Behavioral/Social Intervention

5.1 Study Intervention Description

The study intervention is supply of baby products. The intervention group (n=5) in this study will be assigned use of phthalate- and bisphenol-free baby products and subscription to a cloth diaper service. Participants assigned to the control group (n=5) will receive disposable diaper delivery and conventional baby products.

5.1.1 Administration of Intervention

This intervention (supply of baby products) will be delivered via mail and/or delivery service. The frequency of delivery will depend on the delivery service. The delivery will cover three months' worth of diapers and baby products.

6 Study Procedures and Schedule

6.1 Study Procedures/Evaluations

6.1.1 Study Specific Procedures

Biospecimen Collection:

- Biospecimens (1.8mL of maternal breast milk, 1.8mL of maternal urine, and 1.8 mL of infant urine) will be collected at one study visit approximately 2-3 months after enrollment. Biospecimen collection will occur either after a routine well-visit or at the participant's home. If a home visit occurs, study staff will go to the participant's home. Refer to Section 6.2 for more details.

Data Collection:

- Participant's electronic medical record will be used to monitor when they have delivered.
- Either the infant's medical record or the NYU CHES study records will be used to obtain birth weight and length for analysis.
- NYC CHES study questionnaire data that participants previously completed under the NYU CHES study will be pulled from the NYU CHES study database.

CONFIDENTIAL

- We will create a new database for the Diaper Study where we will store all Diaper Study-related results along with demographic and NYU CHES study questionnaire data to be pulled from the NYU CHES database.

Questionnaire Administration:

- Participants will be asked to complete a brief adherence questionnaire at three postpartum time points.
 - Questionnaire will be administered over the phone by study personnel 2 weeks and 6 weeks after diaper intervention has begun.
 - Questionnaire will also be administered during the single study visit.
- It will take less than 5 minutes to complete questionnaire.
- Questionnaire responses will be entered into REDCap by study personnel.
- The purpose of the questionnaire is to assess if the diaper delivery service is working smoothly for the mother and to gauge adherence to group assignment.
- Questionnaire data collected from this study will be shared with qualified researchers on the NYU CHES study.

6.1.2 Standard of Care Study Procedures

No clinical procedures are carried out in this study.

6.2 Study Specific Biospecimens

6.2.1 Specimen Collection Procedures

Participants will be asked to manually express breast milk into a polypropylene specimen cup (Starplex Scientific Corp., Cleveland, TN).

Maternal urine will be collected via standard procedure in a sterile cup.

To collect infant urine, a Pediatric Urine Collector (Precision Dynamics Corp., Valencia, CA) will be provided to participants. This device is composed of a clear plastic bag with a foam-lined opening that adheres to the skin around the infant's genital area without puckering, providing a leak-proof seal.

Diaper Study personnel will not be involved in the maternal specimen collection procedures. Diaper Study personnel will facilitate the collection of infant urine.

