Brief Summary	Phthalates and bisphenols have been detected in a range of infant care products. This pilot study will test whether intervening on these sources of exposure during the critical period of minipuberty affects infants' body burden of phthalates and bisphenols. We will recruit 10 participants from the ongoing NYU Children's Health and Development Study (CHES) cohort study who are >=37 weeks gestation or <6 months postpartum, carrying a singleton fetus or with a singleton infant, and intending to breastfeed or breastfeeding. We will randomly assign them to use either conventional baby products or phthalate- and bisphenol-free baby products for the first or next three months of their children's lives. Toward the end of the intervention, we will collect maternal breast milk and infant urine, and assay samples for phthalate metabolite and bisphenol concentrations.
Phase	N/A
Objectives	Aim 1: To assess the feasibility of an intervention designed to reduce infant phthalate and bisphenol exposure Aim 2 (exploratory): To compare urinary phthalate and bisphenol exposure levels in the intervention and non-intervention groups, as well as between mothers and children in the control group.
Methodology	Open-label randomized controlled trial

Endpoint	Participants are enrolled until they have been using the assigned diapers for 3 months, toward the end of which time we will collect maternal breast milk and maternal and infant urine to test for phthalate metabolite and bisphenol concentrations
Study Duration	1 year (allows for 6 months of data collection among 10 participants and 6 months of data analysis).
Participant Duration	3 months
Population	We will recruit 10 participants who are already enrolled in the NYU CHES study at the Brooklyn campus. Eligible participants will be ≥ 37 weeks gestation or < 6 months postpartum, carrying a singleton fetus or with a singleton infant, and intending to breastfeed or breastfeeding.
Study Site	NYULH-Brooklyn
Number of participants	10 participants
Description of Study Intervention/Procedure	Half of the participants will be randomly assigned to the intervention group and will receive a three-month supply of phthalate- and bisphenol-free baby products (e.g., wipes, diaper cream) and a subscription to a cloth diaper service.

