Reference Therapy	Half of the participants will be randomly assigned to the control group and provided with a three-month supply of conventional disposable diapers (e.g., Huggies or Pampers) and baby products (e.g., wipes, diaper cream).
Key Procedures	Three-month adherence to diaper assignment and one-time infant urine collection and maternal breast milk collection.
Statistical Analysis	Our primary aim is to assess the feasibility of the intervention; the project is not adequately powered to detect statistically significant differences between groups. However, we will compare distributions of chemicals between the two infant groups to assess the effectiveness of the intervention and also between mothers and children from the control group to assess the relative prevalence of particular bisphenols or phthalates in diet (reflected in maternal breast milk concentrations) vs. baby products (reflected in infant urinary concentrations).

CONFIDENTIAL

Schematic of Study Design

Key Roles

[name], MPH (Principal Investigator)

Assistant Professor, Department of Pediatrics, NYU Grossman School of Medicine
[name]
[contact]
[contact]

[name] (Sub-Investigator)

Pediatrics, Environmental Medicine & Population Health, NYU Grossman School of Medicine
Director and PI of NYU CHES Study
[name]
[contact]
[contact]

[name], MS (Sub-investigator)

Research Scientist, Lab Manager, Department of Pediatrics, Division of Environmental Pediatrics, NYU Grossman School of Medicine
[name]
[contact]
[contact]
(Analyze phthalate and bisphenol levels in urine and breast milk)

[name] (Sub-Investigator)

Research Data Associate, Department of Pediatrics, Division of Environmental Pediatrics, NYU Grossman School of Medicine
[name]
[contact]
[contact]
(Recruitment, consenting, project management, and data collection)

[name] (Study Team Member)

Assistant Professor, Department of Pediatrics, NYU Grossman School of Medicine
[name]
[contact]
[contact]
(Assist in analysis of urine and breast milk)

CONFIDENTIAL

This material is the property of the NYU Langone Health. Do not disclose or use except as authorized in writing by the study sponsor
Behavioral Intervention Template Version: 18 July 2022

1 Introduction, Background Information and Scientific Rationale

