1.2 Rationale

Infants are highly exposed to phthalates and bisphenols, ubiquitous EDCs that have both estrogenic and anti-androgenic activity. Phthalates and bisphenols have been detected in a range of infant care products, including diapers,^{17,18} wipes, baby lotions, soaps, shampoos,¹⁹ and plastic baby bottles.²⁰ Exposure is magnified by infants' high surface-to-volume ratio and by the increased efficiency of dermal absorption via the thin skin surrounding their enlarged genitalia.²¹ This pilot study will test whether intervening on these sources of exposure during the critical period of minipuberty affects infants' body burden of phthalates and bisphenols. If successful, this protocol may be scaled up and eventually evidence may be used to inform regulation of chemicals contained in infant care products and educational outreach programs to protect children's health.

Aim 1: To assess the feasibility of an intervention designed to reduce infant phthalate and bisphenol exposure.

H1: We will successfully recruit participants from within an existing cohort study and collect biosamples from participants and their children in a single follow-up study visit.

Aim 2 (exploratory): To compare urinary phthalate metabolites and bisphenols between the intervention and non-intervention groups, as well as between mothers and children in the control group.

H2: Chemical levels will be higher among infants in the control group vs. the intervention group. There will be no difference in average chemical concentrations between the two groups of mothers. Among controls, different chemicals will be present in breast milk vs. infant urine.

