1.3 Potential Risks & Benefits

1.3.1 Known Potential Risks

There is no excess risk to participants in this study due to the intervention being tested, which is designed to reduce the risk of endocrine disruption. The phthalate- and bisphenol-containing disposable diapers and baby products that the control group will receive are by far the standard in the US. We hypothesize that the phthalate- and bisphenol-free diapers and baby products that the intervention group will receive will reduce their risk of health outcomes associated with EDC exposure.

There is a risk of loss of confidentiality or privacy in relation to personal information and specimens to be collected upon participation in this study. We will make every effort to protect participants' privacy by labeling their samples and information only with a code, and keeping the key to the code in a password-protected database accessible only to IRB-approved study personnel.

There is no excess risk to participants associated with completing questionnaires. Participants may feel frustrated from answering questions. If that happens, participants are free to skip any questions they do not wish to answer.

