6.2.2 Specimen Preparation, Handling, and Storage

Urine and breast milk will be aliquoted into bisphenol- and phthalate-free 2 mL tubes (Thermo Scientific, Waltham, MA) within two hours of collection and will be stored at -80°C. Urine and breast milk collection containers/devices will be tested for the presence of phthalates and bisphenols.

CONFIDENTIAL

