6.3.5 Study Visit

- After using products in assigned study group for up to three months, a single study visit will occur after a routine well-visit or at participant's home between 2 and 3 months after diaper intervention has begun. If visit cannot occur after infant's well-visit, Diaper Study team member will go to participant's home.
- Diaper Study team member will confirm consent.
- Participants will be asked to provide maternal breast milk and urine samples.
- Diaper Study team member will collect infant urine sample.
- Participants will complete questionnaire.

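### Infant urine is bagged on diaper-area skin with no skin-preparation step, so any bisphenol residue from conventional products could raise control values without absorption

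*Combined protocol and SAP*

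**What the plan says.** The question in Section 1.2 is whether changing infant care products "affects infants' body burden of phthalates and bisphenols". The outcome is measured once per infant. Under Section 6.3.5 the visit takes place "between 2 and 3 months after diaper intervention has begun", which is within the three-month product supply.

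Section 6.2.1 describes the collector as "a clear plastic bag with a foam-lined opening that adheres to the skin around the infant's genital area". On who does what, it says "Diaper Study personnel will facilitate the collection of infant urine"; Section 6.3.5 has a team member collect the sample. Neither section says how the skin is cleaned first, with what, or whether the assigned wipe or cream may be used at that diaper change.

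The arms differ in what touches that skin. The Protocol Summary gives the intervention arm a "three-month supply of phthalate- and bisphenol-free baby products (e.g., wipes, diaper cream) and a subscription to a cloth diaper service". The control arm receives conventional disposable diapers, wipes and cream. Section 1.3.1 says: "The phthalate- and bisphenol-containing disposable diapers and baby products that the control group will receive are by far the standard in the US".

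The contamination check at collection is in Section 6.2.2: "Urine and breast milk collection containers/devices will be tested for the presence of phthalates and bisphenols". The same section specifies storage tubes free of both chemical classes.

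**The concern.** Body burden means chemical that the infant has absorbed. The specimen is urine that passes over diaper-area skin into a bag sealed to that skin. If conventional products leave bisphenol there, some of it can wash into the bag and be counted as urinary bisphenol.

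This differs from ordinary background contamination. Bisphenol shed by the bag itself would affect both arms alike and would largely cancel in the comparison. Residue from the assigned products would occur in one arm only. On the protocol's own description of the products, it would push control values up, as the Aim 2 hypothesis in Section 9.2 predicts. Section 1.2 proposes absorption through the skin around the genitalia, so true exposure and surface carry-over would come from the same products at the same site. The bisphenol measurement as described cannot separate them.

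Two planned analyses are at stake. One is the t-test between infant groups in Section 9.4.2. The other is the control-arm comparison of breast milk, read as diet, with infant urine, read as baby products. Residue would enter only the urine side of that comparison.

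**Working it through.** The plan has no figure to reproduce. Section 9.4.5 sets the sample at 5 per group on budget, and no alpha, SD or effect size is stated.

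**1. Is there an arm-dependent source at sampling?** The products are supplied for three months and the visit is at 2 to 3 months, so they are expected to be in use. By the protocol's description, the control products contain bisphenols and the intervention products do not. A source that differs by arm is therefore possible.

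**2. Would a planned check detect it?**
- Device and container testing (6.2.2) examines materials common to both arms, not skin.
- Section 11 lists calibration checks, method controls, fortified samples and duplicates. These verify the assay, not what entered the bag.
- Creatinine adjustment (6.2.4) corrects for urinary dilution and does not subtract added residue.
- No field blank and no split of free from conjugated bisphenol is described.

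None of these would show residue.

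**3. Which analytes are exposed?** Section 6.2.4 lists 8 bisphenols and 22 phthalate metabolites, 8 + 22 = 30 in all. The bisphenols are measured as the compounds themselves, so residue would be read as the analyte. For phthalates the analytes are metabolites, so parent phthalate on the skin is not what is measured. Carry-over would need a further step, such as conversion in the sample, that the documents do not describe. The direct route covers at most 8 of 30 analytes and the bisphenol sum.

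**4. How much residue would matter?** Inputs: bisphenol limits of detection (LOD) of 0.04-0.50 ng/mL (Section 11) and an infant specimen of 1.8 mL (Section 6.1.1). Residue mixes with the whole void, whose volume V is not stated. The mass that adds one LOD is LOD x V.

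| V | at 0.04 ng/mL | at 0.50 ng/mL |
|---|---|---|
| 1.8 mL (void equals specimen, smallest case) | 0.072 ng | 0.90 ng |
| 10 mL (assumed) | 0.4 ng | 5 ng |
| 30 mL (assumed) | 1.2 ng | 15 ng |

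**5. How sensitive is the planned comparison?** This simulation assumes 5 per arm, log concentrations, equal true levels in both arms, residue added to controls only, two-sided alpha 0.05 and 40,000 runs. Residue size and geometric SD (GSD) are assumptions. Entries are the apparent control/intervention geometric mean ratio, then the share of runs with p<0.05.

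| Median residue / true median | GSD 2 | GSD 3 |
|---|---|---|
| 0 | 1.00; 5.0% | 1.00; 4.9% |
| 0.5 | 1.66; 21.1% | 1.89; 14.7% |
| 1 | 2.23; 45.2% | 2.56; 26.9% |
| 3 | 4.35; 90.5% | 4.91; 60.7% |

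Section 9.4.2 does not state the scale. On the raw scale the shares are lower, for example 38.1% and 16.7% at a ratio of 1. The table shows what residue of a given size would do. It does not say that residue of that size occurs.

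**The case against.** The best defence is that the mechanism is possible but not shown. Several parts of it stand.

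- **Product content.** Section 1.2 reports phthalates and bisphenols jointly across a list of products that includes wipes but not diaper cream. Section 1.3.1 labels the control products as a class. Nothing says which bisphenol is in which product. A reader might infer that all eight bisphenols are inflated, but the documents support only those that the conventional products leave on the skin.
- **Phthalates.** A reader might extend the point to every urinary difference between arms. The 22 metabolites are outside the direct route.
- **Direction and certainty.** A reader might conclude that control values are always biased upward, or that a bisphenol difference could never be interpreted. The protocol is silent on cleaning. That shows an unspecified step, not a step known to differ between arms. Staff take part in collection, possibly just after a well-visit, and may already clean every infant in the same way.
- **Size.** The 0.07-0.9 ng figures treat the specimen as the whole void. They are the smallest case and say nothing about how much residue is present.
- **Consequence.** Aim 2 is exploratory, the study is declared underpowered, and the primary aim is feasibility. No confirmatory claim depends on this comparison.

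None of this fills the gap. No planned check could show that residue is absent. A larger follow-on trial using the same collection method would carry the same bias, since a larger sample does not remove it.

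**Conclusion.** The point holds for bisphenols, as a possible bias of unknown size that differs by arm. It rests on three things: the protocol's own description of the control products as bisphenol-containing, product use continuing up to the visit, and the absence of any stated skin-preparation step. If residue reached the sample, it would raise control bisphenols without absorption and act in the direction of the hypothesis. It would also affect the control-arm comparison of infant urine with breast milk.

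As little as 0.07-0.9 ng would add one LOD in a 1.8 mL void, and proportionally more in a larger one. Whether that much is present cannot be learned from the documents. The point does not touch the feasibility aim and does not make the bisphenol results uninterpretable. It is an inexpensive improvement to a comparison that Section 9.4.2 uses to judge effectiveness and that Section 1.2 sees as a basis for scaling up.

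**What to change.** Add one step to Section 6.2.1, identical in both arms: before the bag is applied, use no assigned wipe or cream at that diaper change, and clean the area with water and gauze. In Section 6.2.2, add the gauze lot to the materials tested, so that it is checked for bisphenols along with the devices.

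This removes application of an arm-specific product immediately before bagging and makes the handling the same in both arms. It should reduce older residue but cannot prove that none remains. A skin-rinse blank could test that, but it is optional: it is a further procedure for each infant, adds up to 10 assays to a study sized by budget, and would need a threshold for calling a blank positive.

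The cleaning step costs a few minutes at the existing visit, one additional material to test, and a minor protocol amendment, which Section 12.2 requires the IRB to approve before it takes effect.
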